Long-term Effects of Individualized Follow-up with an App for One Year

NCT05697120

Date: 28th of August, 2023

Statistical analyses plan

The present study is a follow up study of a completed study registered at ClinicalTrials.gov with the following ID: NCT03174106. Some of the data (i.e. baseline characteristics) will be analysed in accordance with previous plan which have been published as results from the RCT and in the published protocol:

IBM SPSS Statistics, Stata, R or other appropriate software will be used for statistical analysis. Continuous, normally distributed baseline data were analysed with an independent t-test to test for differences between groups, and Pearson's chi squared test was used to analyse the categorical data. Baseline differences between cases with and without one-year primary outcome data were analysed using the same statistical tests. For the present follow-up study, the same statistical tests will be used to test for baseline differences between cases with and without five-year primary outcome data. The assessment of missing data will be done based on strategies for dealing with missing data in clinical trials (Dziura et al. 2013).

The data will be analysed in accordance with the intention-to-treat principle. Differences between groups will be assessed using linear mixed models for repeated measurements. We will use a subject-specific random intercept and maximum likelihood estimation with the respective outcome measurement at baseline (post-cardiac rehabilitation). Group (intervention and control), time and the interaction between group and time will be fixed effects as outlined by Twisk (2021). The underlying structure of the model estimates the outcome at each visit (post intervention and 5-year follow-up). We might include additional analysis to explore the change from baseline. P-values ≤ 0.05 will be considered as statistically significant and all tests will be two sided.

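### With a random intercept as the only stated covariance component, the 5-year standard error is valid only if the 1-year and 5-year variances are equal

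*SAP*

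**What the plan says.** The SAP has one paragraph on the between-group analysis. It states that "Differences between groups will be assessed using linear mixed models for repeated measurements". On the covariance it says only "We will use a subject-specific random intercept and maximum likelihood estimation". That sentence goes on to mention the baseline value of the outcome, but does not settle whether baseline is a covariate or a further outcome row. Group, time and their interaction are the fixed effects, with a textbook chapter cited for them. On visits it says "The underlying structure of the model estimates the outcome at each visit (post intervention and 5-year follow-up)". The decision rule is "P-values ≤ 0.05 will be considered as statistically significant and all tests will be two sided".

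The paragraph before it leaves the software open and expects missing 5-year data, since the plan is to "test for baseline differences between cases with and without five-year primary outcome data". The SAP gives no SD, correlation, sample size or expected missing rate.

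**The concern.** A random intercept with one residual variance gives every visit the same variance. The SAP does not exclude visit-specific residual variances, but it does not provide for them, and an analyst who follows the text with common software settings would fit a single one.

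Equal variance is doubtful here. If baseline is a covariate, what matters is the variance left after adjusting for baseline. Baseline probably predicts the 5-year value less well than the 1-year value, which leaves more variance at 5 years. The pooled variance would then be too small for the 5-year contrast.

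That contrast is what this follow-up study adds. If its SE is too small, a sustained effect may be claimed falsely. If the 5-year variance is the smaller one, the SE is too large and power is lost.

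**Working it through.** The SAP has no design figure to reproduce. Its only number is the two-sided 0.05 threshold, used here as the reference. Everything else below is an assumption shown over a range.

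**1. Baseline as covariate, two follow-ups, complete data.** Let V1 and V5 be the variances given baseline, and r = SD(5 years)/SD(1 year), so V5 = r²·V1. The model uses about (V1 + V5)/2 at 5 years, while the true variance is V5. Hence:

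- R = model SE / true SE = √[((1 + r²)/2) / r²]
- true type I error = 2·Φ(−1.96·R)

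Example, r = 1.25: r² = 1.5625; (1 + 1.5625)/2 = 1.28125; 1.28125/1.5625 = 0.82; R = 0.906; type I error = 7.6%.

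| r | R | Type I error | 95% CI coverage |
|---|---|---|---|
| 0.8 | 1.13 | 2.7% | 97.3% |
| 1.0 | 1.00 | 5.0% | 95.0% |
| 1.1 | 0.96 | 6.1% | 93.9% |
| 1.25 | 0.91 | 7.6% | 92.4% |
| 1.5 | 0.85 | 9.6% | 90.4% |

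**2. The same in terms of correlation with baseline.** If the total variances at the two visits are equal, r² = (1 − c5²)/(1 − c1²), where c1 and c5 are the correlations of the 1-year and 5-year values with baseline.

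- c1/c5 = 0.5/0.4: r² = 0.84/0.75 = 1.12; type I error 5.7%
- 0.7/0.6: r² = 0.64/0.51 = 1.25; 6.3%
- 0.8/0.6: r² = 0.64/0.36 = 1.78; 8.3%

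**3. Simulation.** Two simulations, both with baseline as covariate (slope 0.7), an assumed 50 per arm, no true effect, 5-year values missing completely at random, maximum likelihood and a normal reference. Simulation A: correlation of 0.5 between follow-ups given baseline, 4,000 replicates per scenario, Monte Carlo SE about 0.3 to 0.5 points. Simulation B: correlation of 0.6, 1,500 replicates (complete data) or 1,000 (30% missing), Monte Carlo SE about 0.4 to 1.1 points. Type I error of the random-intercept model (a dash means no result):

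| r | A, complete | A, 30% missing | B, complete | B, 30% missing |
|---|---|---|---|---|
| 0.8 | 3.4% | 2.7% | 3.0% | 3.3% |
| 1.0 | 5.8% | 5.9% | 5.8% | 6.7% |
| 1.1 | 6.9% | 6.8% | – | – |
| 1.25 | 8.3% | 8.7% | 8.6% | 9.2% |
| 1.5 | 10.4% | 11.5% | – | 13.4% |

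With unstructured covariance on the same data, type I error is 5.3% to 6.5% in A. In B it is 5.4% to 5.9% with complete data (r from 0.8 to 1.25) and 6.4% to 7.0% with 30% missing. There is no trend with r. The remaining excess over 5% comes from maximum likelihood with a normal reference, since both models show it when the variances are equal. Missing 5-year values make matters worse at r = 1.25 and 1.5 because the pooled variance then leans towards the 1-year visit.

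**4. Baseline as a third outcome row, complete data.**

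- *Group-by-time unconstrained.* The 5-year difference is the raw mean difference, and the model variance is the average of the three visit variances. With equal total variances the SE is correct. If the 5-year SD is 1.25 times the SD at the other two visits, R = √[(2 + 1.5625)/(3 × 1.5625)] = √0.76 = 0.872 and type I error is about 8.8%.
- *Baseline means constrained equal, total variances equal.* Let m be the mean of the three pairwise correlations. The model variance is proportional to 1 − m² and the true variance to 1 + m² − 2·m·c5. For correlations (baseline–1 year / baseline–5 years / 1–5 years) of 0.7/0.5/0.6: m = 0.6, model 0.64, true 0.76, R = 0.918, type I error 7.2%. For 0.5/0.4/0.5 and 0.8/0.6/0.7 it is 5.9% and 8.3%. For three correlations all equal to 0.6 it is 5.0%.

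**The case against.** The strongest reply is that the fault depends on two things the SAP does not state: a single residual variance, and unequal variances. A random intercept is a conventional choice. With baseline as covariate and two follow-ups, its one correlation is free, so only equal variance is imposed. With complete data the 5-year point estimate is unaffected. The cited chapter might also give a residual structure.

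The first part stands as a limit: this is a conditional weakness, not a proven error. It does not remove the concern, because the plan should protect the 5-year contrast whether or not the variances turn out equal. The chapter cannot be consulted here; the SAP attaches it to the fixed effects, and nothing in the SAP's own text supplies a residual structure.

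The larger figures also need care. Under equal total variances, r = 1.5 requires c1 above √(1 − 1/2.25) = 0.745, and at c1 = 0.8 it requires c5 = √(1 − 2.25 × 0.36) = 0.44. The correlation examples, at 5.7% to 8.3%, are therefore the more realistic guide unless total variance also grows. The simulated rates include roughly one point (up to nearly two in simulation B with 30% missing) that is unrelated to the covariance structure. Finally, if baseline is an outcome row with an unconstrained interaction and total variances are equal, the visit-level contrast from complete data has the right SE. These points reduce the likely size but leave the direction and the remedy unchanged.

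**Conclusion.** The concern holds as a conditional one. As written, the validity of the 5-year SE, confidence interval and P-value rests on equal variances, which the SAP neither justifies nor plans to check. For SD ratios of 0.8 to 1.5 given baseline, true type I error runs from 2.7% to 9.6% analytically, with modest inequality giving modest error (6.1% at a ratio of 1.1). With 30% of 5-year data missing and a ratio of 1.5, the simulations give 11.5% and 13.4%. The SD ratios, correlations, sample size and missing rate are all assumed, and a single residual variance is taken as the usual default. Confidence is medium, because the trial's actual variances are unknown. The change is worth making because it is cheap and protects the main new result.

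**What to change.** Replace the random-intercept-only specification with an unstructured covariance across the modelled visits, and report the 5-year contrast from that model. Alternatively, keep the random intercept and state either visit-specific residual variances or robust SEs. Unstructured is the safer choice if baseline is an outcome row, because visit-specific residual variances with a random intercept still force equal covariances between visits. The same sentence should say whether baseline is a covariate or an outcome row.

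The cost is one sentence of SAP text and one software option, with no new data. With baseline as covariate there are three covariance parameters instead of two; with baseline as a third row there are six instead of two. The choice should be fixed before the 5-year data are analysed. REML with small-sample degrees of freedom would address the small excess that both models show under equal variances, but that is a separate refinement.

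### The SAP leaves the role of the baseline outcome in the mixed model unclear and lists no baseline-by-time term; under two conditions that it neither shows nor excludes, this would bias the 5-year group difference

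*SAP*

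**What the plan says.** The relevant text is the linear mixed model paragraph of the SAP.

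- Random part and estimation: "We will use a subject-specific random intercept and maximum likelihood estimation".
- Baseline: the same sentence goes on to "maximum likelihood estimation with the respective outcome measurement at baseline (post-cardiac rehabilitation"). It does not say whether baseline is a covariate, an additional outcome row or something else.
- Fixed effects: "Group (intervention and control), time and the interaction between group and time will be fixed effects", with reference to a cited textbook chapter. Neither baseline nor baseline-by-time is in the list.
- Modelled visits: "The underlying structure of the model estimates the outcome at each visit (post intervention and 5-year follow-up"). Baseline is not among them, which favours the covariate reading.

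On missing data, the preceding paragraph says that "the same statistical tests will be used to test for baseline differences between cases with and without five-year primary outcome data". No comparison by arm is stated. The SAP gives no sample size, withdrawal rate, SD or correlation between visits.

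**The concern.** The 5-year group difference is the new result of this follow-up study. Adjustment for baseline should protect it when the people still seen at 5 years differ at baseline between the arms. That protection depends on the slope used at 5 years being right.

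With a single slope for both visits, the estimate is a compromise. It leans towards the post-intervention visit, where more people are observed. A measurement usually predicts a near visit better than one several years later. If that holds here, the shared slope is too steep at 5 years. Suppose less fit controls withdraw more often than less fit intervention participants. The controls who remain then have the better baseline values, the model over-corrects for this, and the error favours the intervention.

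This is a fault of the mean model. It can occur when data are missing at random given baseline and arm, and a freer covariance structure does not remove it.

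**Working it through.** The SAP states no figure to reproduce. Every number below is an assumption or follows from one.

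**Size of the error.** Write b1 and b5 for the true baseline slopes at 1 and 5 years, b for the shared fitted slope, r for the fitted within-person residual correlation, and g for the baseline difference (intervention minus control) among those seen at 5 years. Suppose everyone is seen at 1 year, the arms are balanced at baseline and the true effect is zero. Then

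bias at 5 years ≈ [(b5 − b) − r(b1 − b)] × g.

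The first term is the wrong slope at 5 years. The second arises because the model borrows from 1-year residuals, which carry the misfit at that visit. If b1 = b5, then b equals both and the bias is zero. If g = 0, the bias is also zero. Both conditions are therefore needed.

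**Numbers put in.** SD 1 at each visit, so slopes equal correlations. Baseline-dependent withdrawal in the control arm only, with g about −0.3. Approximate r by the residual covariance over the mean residual variance.

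- Correlations 0.85 (baseline to 1 year), 0.70 (baseline to 5 years), 0.75 (1 to 5 years); fitted b = 0.80. Residual covariance 0.75 − 0.85 × 0.70 = 0.155. Residual variances 1 − 0.85² = 0.2775 and 1 − 0.70² = 0.51, mean 0.394. So r ≈ 0.39. Bias ≈ [−0.10 − 0.39 × 0.05] × (−0.3) = 0.036.
- Correlations 0.85, 0.60, 0.70; fitted b = 0.77. Residual covariance 0.70 − 0.85 × 0.60 = 0.19. Residual variances 0.2775 and 0.64, mean 0.459. So r ≈ 0.41. Bias ≈ [−0.17 − 0.41 × 0.08] × (−0.3) = 0.061.

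**Simulation under these assumptions.** Zero true effect, about 36% without 5-year data, random-intercept model by maximum likelihood, 55 per arm, 1,500 runs per scenario. Size of the 5-year bias in SD:

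| Correlations (base-1y, base-5y, 1y-5y) | Shared slope, one arm | Shared slope, opposite directions |
|---|---|---|
| 0.85, 0.70, 0.75 | 0.038 | 0.054 |
| 0.85, 0.65, 0.70 | 0.049 | 0.070 |
| 0.85, 0.60, 0.70 | 0.062 | 0.096 |

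The one-arm figures in the first and last rows agree with the hand calculation. With baseline-by-time added, bias is −0.001 to 0.005. With an unstructured covariance but no interaction it remains, at 0.043 to 0.112.

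**A second set of assumptions.** Baseline SD 1, 1-year slope 0.8, residual SDs 0.6 and 0.8 with correlation 0.5, about 30% missing at 5 years, very large sample. Here low-baseline intervention participants withdraw more, so g is positive and the bias negative.

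| 5-year slope | One arm (g ≈ 0.23) | Opposite directions (g ≈ 0.46) |
|---|---|---|
| 0.8 | 0.001 | 0.001 |
| 0.7 | −0.017 | −0.037 |
| 0.6 | −0.034 | −0.075 |
| 0.4 | −0.071 | −0.142 |

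When withdrawal is unrelated to baseline, or related in the same way in both arms, the bias is at most 0.003 for any of these slopes. Adding baseline-by-time brings it to at most 0.003 throughout.

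**Against the sampling error.** With 120 participants in all, the second set gives 0.035/0.170 = 0.2 of the sampling SD (slope 0.6, one arm), 0.074/0.175 = 0.4 (slope 0.6, opposite) and 0.144/0.182 = 0.8 (slope 0.4, opposite). A shift of 0.2 to 0.5 standard errors by itself would move a nominal 5% two-sided test to about 5.5% to 8%: Φ(−1.76) + Φ(−2.16) = 0.055 and Φ(−1.46) + Φ(−2.46) = 0.079.

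**If baseline were left out**, as the bare list reads, the second set gives biases between −0.051 and 0.089 when withdrawal differs by arm. The value 0.089 arises with equal slopes and opposite withdrawal.

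**The case against.** The strongest reply is that the document shows neither condition. It gives no slopes or correlations, and a lower slope at 5 years, though plausible, is an assumption. It also contains nothing to suggest that withdrawal relates to baseline differently by arm. This stands, and it limits the point to a conditional one.

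Second, the shared slope is itself inferred. The fixed-effects list does not contain baseline, and the sentence defers to a cited textbook chapter that may set out the model more fully. This also stands. It makes the unclear role of baseline the more basic gap, and the deferral does not close that gap, because the SAP names its own terms without placing baseline among them.

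Third, a common baseline coefficient is a conventional choice and the likely bias is modest. That is fair. It argues for low severity, but not against a change that costs almost nothing.

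A reader might infer three stronger claims that the SAP does not support:

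- *That withdrawal differing by arm is enough to bias the result.* With equal slopes the bias was 0.001, even with withdrawal in opposite directions.
- *That the SAP expects selective withdrawal.* It plans a check, repeating one done at one year. Planning a check does not predict its result.
- *That chance baseline imbalance causes the same bias.* Under randomisation such imbalance averages to zero and produces no systematic error.

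**Conclusion.** The point holds in conditional form and is of low severity. The SAP does not say clearly how baseline enters the model, and it names no baseline-by-time term. If baseline is a covariate, one slope serves both visits. If, in addition, the true slope changes between visits and withdrawal depends on baseline differently by arm, the 5-year difference is biased by about 0.03-0.10 SD, roughly 0.2-0.5 standard errors. That range rests on the assumed correlations, about 36% missing and 55 per arm. The second set of assumptions gives values as low as 0.017 for a small change in slope and as high as 0.142 for a slope that halves with opposite withdrawal. If either condition fails, there is no bias. Nothing here shows that the planned estimate is in fact biased.

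**What to change.** Replace the fixed-effects sentence with: *Baseline outcome, group, time, group-by-time and baseline-by-time will be fixed effects, and the 5-year group difference is estimated from this model.* This settles the role of baseline and gives each visit its own slope.

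The cost is one extra parameter per outcome relative to the shared-slope model, and no new data. Precision is essentially unchanged: the empirical SD of the 5-year estimate stayed within about 0.005 of the shared-slope model in the first simulations, and in the second it went from 0.170 to 0.168 and from 0.175 to 0.176 in the two scenarios with a 5-year slope of 0.6. If the true slopes are equal, the added term introduces no bias.

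### Does leaving the decisive contrast unnamed, with an optional change-from-baseline analysis and one 0.05 threshold, let a 5-year claim rest on 1-year data or a chosen test?

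*SAP*

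**What the plan says.** All the relevant text is in the SAP's last paragraph before the reference list, apart from the cited publications and the missing-data comparison.

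- Comparison: "Differences between groups will be assessed using linear mixed models for repeated measurements".
- Model terms: "Group (intervention and control), time and the interaction between group and time will be fixed effects as outlined by Twisk (2021"). The outcome's baseline value also enters the model, with a subject-specific random intercept.
- What the model delivers: "The underlying structure of the model estimates the outcome at each visit (post intervention and 5-year follow-up").
- Optional extra: "We might include additional analysis to explore the change from baseline".
- Threshold: "P-values ≤ 0.05 will be considered as statistically significant and all tests will be two sided".

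The 1-year data have already been examined: "Baseline differences between cases with and without one-year primary outcome data were analysed using the same statistical tests". The title of the cited trial report gives the direction of that result: "Long-term follow-up with a smartphone application improves exercise capacity post cardiac rehabilitation". The SAP then says that cases with and without the primary outcome at five years will be compared at baseline, so it presupposes a primary outcome measured at that visit. It gives no sample size, effect size, standard deviation or correlation.

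**The concern.** A model with group, time and group-by-time can produce several group tests: the group coefficient (whose meaning depends on how time is coded), an average over both visits, the interaction, and a contrast at each visit. The SAP does not say which one answers the long-term question, and the same 0.05 applies to all of them. It also keeps open a further analysis of the same outcome.

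One of the two modelled visits is already known and, by the cited title, favourable for exercise capacity. An average over visits would carry that known result into a statement about persistence. A non-significant interaction could be read as a maintained effect although it may only reflect low power. If the choice among these were made after seeing the data, the study could report a lasting effect when none exists at 5 years.

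**Working it through.** **Plan's own figure.** The only number to work from is the two-sided 0.05 threshold. There is no derived figure to reproduce.

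**1. Is the 5-year effect in the model?** Write the mean outcome as b0 + b1·baseline + b2·G + b3·T + b4·G·T.

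- T = 0 post intervention, T = 1 at 5 years: the 5-year effect is b2 + b4.
- T = 0 at 5 years: the 5-year effect is b2 itself.
- The average over visits is b2 + b4/2 under either coding.

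The 5-year effect is therefore one coefficient or a simple sum of two. It matches the SAP's description of an estimate at each visit. The average is a further quantity that the SAP does not mention.

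**2. Assumptions for the error rates (none are in the SAP).** 30 or 50 per arm; SD 1; baseline to follow-up correlation r of 0.6–0.8; correlation between the two follow-ups, s, of 0.6–0.8; true 5-year effect zero; true 1-year effect d of 0, 0.3 or 0.5 SD; 200,000 simulated trials per scenario. With v = 1 − r², c = s − r² and se² = 2/n, the variances in units of se² are:

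| Quantity | Variance |
|---|---|
| 5-year contrast, baseline-adjusted | v |
| Average over visits | (v + c)/2 |
| Interaction | 2(v − c) |
| 5-year change from baseline, unadjusted | 2 − 2r |

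**3. What the optional analysis adds.** The correlation between the adjusted 5-year contrast and the unadjusted change contrast is (1 − r²)/√[(1 − r²)·2(1 − r)] = √[(1 + r)/2]. That is √0.80 = 0.89 at r = 0.6 and √0.90 = 0.95 at r = 0.8. The two tests nearly coincide, so either one is significant in 6.4–7.2% of simulated trials, against 9.75% for two independent tests (1 − 0.95²). If the change analysis also adjusts for baseline, subtracting the baseline from the outcome alters only the baseline slope, from b1 to b1 − 1. The group contrast is identical and nothing is added.

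**4. No effect at either visit.**

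| Tests counted | At least one P ≤ 0.05 |
|---|---|
| 5-year contrast | 5% |
| 5-year contrast or change | 6.4–7.2% |
| 5-year contrast or average | 7.5–7.9% |
| 5-year contrast, average or interaction | about 11.4% |
| All four | 12.4–13.0% |

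These count results in both directions. Only half favour the intervention: 2.5% for the 5-year contrast alone, and about 7%/2 = 3.5% with the change analysis added.

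**5. A true 1-year effect that has vanished by 5 years (d = 0.3–0.5).** The average is significant in 14–69% of trials and the interaction in 25–98%. Hand check of the upper end for the average: n = 50, r = s = 0.8 gives v = 0.36 and c = 0.16, so SE = 0.2·√0.26 = 0.102. The expected average is 0.5/2 = 0.25, so z = 2.45 and the rejection probability is P(Z > 1.96 − 2.45) = 0.69. In the same scenarios the 5-year contrast is significant in 4.9–5.1%.

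Restricting to trials with a significant 1-year result (assumed true 1-year z of 2 to 3), the average is significant in roughly 32–51% and the interaction is non-significant in roughly 10–56%, depending on the correlations assumed.

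**6. Which rows describe this plan?** The SAP commits to visit-specific estimates and mentions an exploratory change analysis, which are the first two rows in step 4. The remaining rows and all of step 5, apart from the 5% for the 5-year contrast, need a reporting choice that the SAP does not make.

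**The case for a change.** The strongest reply is that choosing the model term that answers the question is the SAP's own job, and this SAP gives a model without a test. Even if the protocol names a primary outcome and time point, that choice must still be tied to a model term. With half the follow-up data already known, a sentence would close the matter at almost no cost.

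Part of this stands. The SAP does not label the 5-year contrast as confirmatory, and its threshold sentence makes no distinction between main and supportive tests. It does not follow that the choice is open in any way that matters. In a study set up to obtain 5-year outcomes, with a model said to estimate each visit, the 5-year between-group difference is the natural reading. An analyst would have to depart from the text to put an average in its place. The ranking of hypotheses is commonly set in the protocol, which was not available here.

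The interaction gives less cause for worry than it seems. If it is significant because a 1-year benefit has faded, that is evidence against persistence. It misleads only if reported as a 5-year benefit. Treating a non-significant interaction as proof of maintenance would be an error of interpretation that the SAP does not invite.

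**Conclusion.** No change to the plan follows. Followed as written, the SAP yields a baseline-adjusted 5-year contrast whose false-positive rate is 5% regardless of the 1-year effect. The optional change-from-baseline analysis is presented as additional and exploratory. Counted as a second test, it adds at most about 2 percentage points (7.2% − 5% = 2.2), and nothing if it uses the same baseline adjustment.

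The figures of about 12–13%, and the much larger ones when a 1-year effect has vanished, illustrate how results could be misreported and do not measure this plan. They also rest on sample sizes, correlations and effect sizes that the SAP does not give, and the premise of a favourable 1-year result rests on a cited title that covers exercise capacity only. What is left is a missing label, a gap that analysts fill sensibly. This conclusion assumes that the 5-year contrast is reported as the answer to the 5-year question. A report that led with an average over visits or an interaction would be open to criticism on its own account.
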